2.0 OBJECTIVES & ENDPOINTS

2.1 Primary Objective & Endpoint

The primary endpoint is to determine progression free rate at week 12 for patients with soft tissue sarcoma (STS) treated with pazopanib plus oral topotecan. The endpoint will be the time from enrollment to progression, with progression defined as changes in RECIST 1.1 defined imaging, progression in non-target lesions as defined by RECIST 1.1, unequivocal clinical deterioration, or death from any cause.

2.2 Secondary Objectives & Endpoints

- 2.2.1 The objective is to determine the overall response rate for patients with STS treated with combination pazopanib and topotecan. The endpoint is the presence of response (ORR- CR+PR) per RECIST version 1.1 in cohort 1.
- 2.2.2 The objective is to determine the clinical benefit rate (CR+ PR + SD) for patients with STS treated with combination pazopanib and topotecan. The endpoint is the presence of clinical benefit (CR+ PR + SD) per RECIST version 1.1 in cohort 1
- 2.2.3 The objective is to determine median PFR for patients with STS treated with combination pazopanib and topotecan. The endpoint is the time from the first dose of the study treatment until death from any cause, up to a maximum follow-up of two years
- 2.2.4 The objective is to evaluate overall survival (OS) for patients with STS treated with combination pazopanib and topotecan. The endpoint is to determine OS for patients with STS treated with combination pazopanib and topotecan.

- 2.2.5 The objective is to assess safety and tolerability for patients treated with combination pazopanib and topotecan. The endpoint is the presence of all toxicities outlined in NCI CTCAE version 4.03 from time of first treatment.
- 2.2.6 The objective is to estimate the PFR for patients with osteosarcoma treated with combination pazopanib and topotecan. The endpoint for patients with osteosarcoma, time from treatment to progression, based upon changes in RECIST 1.1 defined imaging, progression in non-target lesions as defined by RECIST 1.1, unequivocal clinical deterioration, or death from any cause.
- 2.2.7 The objective is to estimate the PFR for patients with liposarcoma treated with combination pazopanib and topotecan. The endpoint for patients with liposarcoma, time from treatment to progression based upon changes in RECIST 1.1 defined imaging, progression in non-target lesions as defined by RECIST 1.1, unequivocal clinical deterioration, or death from any cause.

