6.5 Primary Endpoint

Time from enrollment to progression, with progression defined as changes in RECIST 1.1 defined imaging, progression in non-target lesions as defined by RECIST 1.1, unequivocal clinical deterioration, or death from any cause.

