6.6 Secondary Endpoints

- The presence of response (ORR- CR+PR) per RECIST version 1.1 in cohort 1.
- The presence of clinical benefit (CR+ PR + SD) per RECIST version 1.1 in cohort 1.
- The time from the first dose of the study treatment until death from any cause, up to a maximum follow-up of two years.
- The endpoint is to determine OS for patients with STS treated with combination pazopanib and topotecan.
- The presence of all toxicities outlined in NCI CTCAE version 4.03 from time of first treatment.
- The endpoint for patients with osteosarcoma, time from treatment to progression, based upon changes in RECIST 1.1 defined imaging, progression in non-target lesions as defined by RECIST 1.1, unequivocal clinical deterioration, or death from any cause.
- The endpoint for patients with liposarcoma, time from treatment to progression based upon changes in RECIST 1.1 defined imaging, progression in non-target lesions as defined by RECIST 1.1, unequivocal clinical deterioration, or death from any cause.

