10.2 Sample Size and Accrual

A total of 92 evaluable STS patients is required to detect 55% vs 66% with 80% power and an alpha level of 10%. If 32 out of the first 55 patients are alive and progression free at 12 weeks, this trial may enroll up to 108 STS patients in order to accrue a total of 92 evaluable patients. If the trial has not yet achieved 32 responses, may be suspended to enrollment to allow the 55th patient to reach week 12 of treatment for evaluation.

In addition, up to 36 patients with osteosarcoma and 20 patients with liposarcoma will be enrolled to obtain exploratory information for patients with these two histologies. Data exists to help construct baseline event free survival outcomes that can be used as a comparison for future phase II trials for recurrent osteosarcoma ([J Clin Oncol](#). 2016 Sep 1;34(25):3031-8. doi: 10.1200/JCO.2015.65.5381. Epub 2016 Jul 11.)

Using a single arm, 2 stage Phase II trial design: For stage I- If 4 or more of 19 patients have disease control of greater than 4 months then Stage 2 should be opened. The endpoint is that if 11 or more patients/ 36 have disease control at 4 months, then the agent is considered sufficiently efficacious for additional study.

As the study has been using 12 week and 20 week endpoints, we can use 20 weeks instead of 16 weeks as a surrogate endpoint.

The DMC reviewed the interim analysis data on 1/11/2017, and has approved cohort 1 to reopen to 96 total patients(to obtain 92 evaluable patients). In addition, based on the percentage of non-evaluable patients during the interim analysis, it was determined that a total of 108 patients would most likely need to be enrolled in order to obtain 92 evaluable patients.

The remaining slots have been equally divided in 5 ways among the sites, with an expiration date of May 12, 2017. Status of accrual will be reassessed at that time, and the remaining slots will be divided accordingly.

The 16 additional osteosarcoma slots will only be available at Northwestern (NMH).

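### Section 2.2.3 labels a death-only endpoint as the STS median PFR, OS is left undefined, and the formal test planned in 10.3 is of a median for which no test is specified

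*Combined protocol and SAP*

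**What the plan says.** Objective 2.2.3 is the median PFR in STS. Its endpoint is "time from the first dose of the study treatment until death from any cause, up to a maximum follow-up of two years". Section 6.6 lists the same text as a secondary endpoint, "The time from the first dose of the study treatment until death from any cause, up to a maximum follow-up of two years", but attaches no median-PFR label to it.

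For overall survival, 2.2.4 says only: "The endpoint is to determine OS for patients with STS treated with combination pazopanib and topotecan". Section 6.6 repeats that sentence. Neither place gives a start, an event, a censoring rule or a horizon.

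The other PFR endpoints are built on progression, and all of them count death from any cause as well:

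- STS primary, 2.1: "The endpoint will be the time from enrollment to progression"; 6.5: "Time from enrollment to progression, with progression defined as changes in RECIST 1.1 defined imaging".
- Osteosarcoma, 2.2.6: "The endpoint for patients with osteosarcoma, time from treatment to progression, based upon changes in RECIST 1.1 defined imaging".
- Liposarcoma, 2.2.7: "The endpoint for patients with liposarcoma, time from treatment to progression based upon changes in RECIST 1.1 defined imaging".

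Section 10.3 plans Kaplan-Meier estimates of PFR and of OS, as two quantities, in each histologic group. Section 10.3 and the Study Summary (Statistical Methodology) also plan one formal hypothesis test, of the median PFR in STS. Sections 10.1 and 10.2 describe a two-stage test of the 12-week progression-free rate: 55% against 66%, 92 evaluable patients, 80% power, alpha 10%. Section 10.1 and the Study Summary make it a one-tailed exact binomial test.

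**The concern.** The objective and the endpoint in 2.2.3 describe different quantities. An analyst who programs the endpoint as written obtains a survival median and reports it as median PFR. OS, which does need a death-based definition, has none. Two secondary results could then come from one survival curve, or the analyst must choose the event, origin and horizon with the data in hand.

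The test in 10.3 adds to this. Its label points to a median, while the design rests on a proportion at a fixed time. A reader cannot tell whether the 12-week test has been misnamed or a further test is intended. The timing matters: the monitoring committee reviewed interim data on 1/11/2017 (10.2), and the Amendment 13 entry in Appendix H says the study is closed to accrual. The wording can still be settled before reporting, but a median test specified now would be post hoc.

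**Working it through.** **1. What PFR means in this protocol.** The abbreviation list expands PFR as progression-free rate, so a median PFR can only be a median progression-free time. Section 1.8 uses it that way: for sorafenib in osteosarcoma it reports a median PFR of 4 months and OS of 7 months, two different times. Side by side:

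| Section | Label | Start | Event |
|---|---|---|---|
| 2.1, 6.5 | STS primary (12-week PFR) | enrollment | progression or death |
| 2.2.3 | STS median PFR | first dose | death only, up to two years |
| 6.6, third item | none | first dose | death only, up to two years |
| 2.2.4; 6.6, fourth item | STS OS | not stated | not stated |
| 2.2.6, 2.2.7 | osteosarcoma and liposarcoma PFR | treatment | progression or death |

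Only 2.2.3 omits progression under a PFR label. Its text has the form of an OS definition, and the OS entry that follows it is empty. Misplaced text is the likely explanation, but that is an inference; the protocol does not say so.

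**2. Scale of the mislabelling.** Inputs from the phase III pazopanib arm in section 1.3: median PFS 4.6 months, OS 12.5 months.

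- Difference: 12.5 − 4.6 = 7.9 months.
- Ratio: 12.5 / 4.6 = 2.7.

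These are another trial's single-agent results. They show how far apart the labelled and the defined quantities can lie; they do not estimate an error in this trial.

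**3. Which STS test is specified.** Inputs from 10.1: n1 = 55, continue with 32 or more successes, n = 92, p0 = 0.55, p1 = 0.66.

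- Early termination under the null: P(X ≤ 31 | 55, 0.55) = 0.6309, which reproduces the stated 63%.
- Exact two-stage rejection probability, success at 57 or more of 92: 0.09998 at 55% and 0.8028 at 66%, which match the stated 10% and 80%.
- Success at 56 or more of 92, as 10.1 is worded: 0.1358 and 0.8431. The choice of cutoff is a separate matter, and nothing here depends on it.

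The stated design figures therefore belong to a binomial test of the 12-week rate. No null median, alternative median, alpha or test statistic for a median appears.

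**4. Can a median test be derived from the 12-week design?** Assume, for illustration, exponential times and 4.345 weeks per month. Median = 12 × ln 2 / (−ln p).

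- p = 0.55: 13.9 weeks, or 3.2 months.
- p = 0.66: 20.0 weeks, or 4.6 months.
- In reverse, a median of 4.6 months gives a 12-week rate of 0.5^(12 / (4.6 × 4.345)) = 0.66.

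The historical 55% rate thus points to a null median of 3.2 months, and the phase III median points to 4.6 months. Under this assumption, 4.6 months is also the median implied by the alternative. The documents do not settle on a null median, so the median test cannot be reconstructed from them.

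**The case against.** The strongest reply is that no analysis is lost. Sections 2.1 and 6.5 define an STS time to progression or death, and 10.3 plans a Kaplan-Meier estimate of PFR for STS, which yields a median if the curve reaches it. That stands. A reader might infer from 2.2.3 that no progression-based median would be produced, but the documents do not support this. The harm is a secondary endpoint whose written definition contradicts its label and those sections.

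The primary conclusion is also safe, since the two-stage decision in 10.1 does not use 2.2.3.

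Three other stronger readings should be set aside:

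- **Section 6.6 as a second mislabelling.** It repeats the death-only text without the median-PFR label. The mismatch is explicit only in 2.2.3.
- **The two-year limit as a contradiction of the follow-up schedule.** The sentence names first dose as its start, and the limit reads naturally from there. Section 4.6 and footnote i to the study procedures plan survival follow-up of 2 years (with PD) or 5 years (without PD), which the footnote counts from last treatment. An analysis limit shorter than data collection is not an error in itself, and a median near 12.5 months would lie well inside 24. What remains open is whether the limit is meant for OS.
- **Section 10.2 as a competing definition of the primary start date.** Its phrase "to allow the 55th patient to reach week 12 of treatment for evaluation" belongs to a rule for suspending accrual. It does not define an endpoint.

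That most readers would guess OS was meant in 2.2.3 does not cure the problem, because OS is then still undefined where it is named. Nor does it explain the median test in 10.3.

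**Conclusion.** The point holds as a correction to the secondary endpoints and the analysis text. It should be fixed, but it does not threaten the primary result. As written, 2.2.3 gives a survival median under a progression label, in conflict with 2.1 and 6.5 and with the separate PFR and OS estimates in 10.3. OS has no operational definition. The formal test named in 10.3 and the Study Summary cannot be run as described, because only the 12-week-rate test is specified for STS. Section 10.2 also has an osteosarcoma go/no-go rule, but it states no alpha or power, and 10.3 plans no formal test in that cohort.

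The size in this trial cannot be computed from the documents. The 7.9-month gap is an outside illustration, and the 3.2 to 4.6 month range of null medians rests on the exponential assumption. The contradiction in definitions and the missing test specification need no assumption; that the 2.2.3 text is misplaced OS wording is only probable.

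**What to change.** 1. In 2.2.3 and 6.6, define the STS endpoint as time to progression (as in 2.1) or death from any cause.
2. In 2.2.4 and 6.6, define OS as time to death from any cause, censored at the date last known alive. State whether the two-year limit from first dose applies to it, given survival follow-up of 2 or 5 years from last treatment.
3. In 10.3 and the Study Summary, name the 12-week-rate test of 10.1 as the formal STS test. Report median PFS and median OS descriptively with 95% confidence intervals. If a median test was intended in addition, specify it fully and label it secondary and post hoc.
4. Document the time origin actually used for the primary endpoint at the 1/11/2017 interim review, and use it for the secondary STS PFS. Do not change the primary origin now: redefining it after interim data were reviewed would be a larger problem than the inconsistency.

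The cost is wording in 2.2.3, 2.2.4, 6.6, 10.3 and the Study Summary, plus one sentence on the time origin. Sample size and treatment are unaffected. The report should state one limit: progression dates will be less precise for patients who stop treatment without PD, because their follow-up is every 6 months and may be by phone.

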2.3 Exploratory Objective & Endpoint

For cohort 1 and 3: Quantify Cell-free circulating tumor DNA (ctDNA) at each time point, and correlate these results with demographic, diagnostic, treatment, and outcomes data.

For cohort 2:

The objective is to estimate the correlation of PFR and OS to levels of sVEGFR2 and PIGF. To meet this endpoint we will collect samples at baseline, 4 weeks, 8 weeks, and 12 weeks to both verify the results of Sleijfer et al and to determine if there is an even earlier correlation that can be detected between levels of these cytokines and PFR as well as OS which may allow us to better predict treatment response early on in therapy.

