4.3 Toxicity Management, Dose Delays/Modifications & Supportive care

Any patient who receives at least one dose of study therapy will be evaluable for toxicity endpoints. Each patient will be assessed for the development of toxicity according to the timeframe referenced in the Schedule of Events table). Toxicity will be assessed according to CTCAE v. 4.03.

After cycle 1 day 1 of therapy, defined as 4 weeks of therapy, cycle 1 day 15, cycle 2 day 1, cycle 2 day 15, cycle 3 day 1, and day one of all subsequent cycles may be administered provided the patient meets the following criteria:

- ANC \geq 1500/mm²
- Platelet count \geq 75,000
- Hemoglobin \geq 9 g/dL (after transfusion if necessary).
- Non-hematologic toxicity recovered to \leq grade 1 or tolerable grade 2
- No evidence of progressive disease

Note: For cycle 1 day 15 and cycle 2 day 15, dosing should only commence AFTER day 15 labs have been reviewed to ensure the above criteria are met. If the patient does not meet the above criteria, study treatment should be held and labs and assessment should be done at least weekly until patient meets the above criteria (patient can be assessed earlier than one week at physician's discretion). If when reassessed, the patient meets the treatment criteria above, proceed with treatment at the dose the patient was receiving during the previous cycle. If patient does not meet the above criteria after a one-week delay, then treatment will continue to be held, and the patient will continue to be evaluated weekly. Treatment can be held for a total of 3 consecutive weeks to allow for treatment related toxicities to resolve. In the case that treatment has been held for 3 weeks for treatment related toxicities, the dose reduction for the next upcoming cycle should be based on the most severe toxicity experienced in the current cycle. If a patient develops another severe toxicity at the reduced dose or if they experience a life-threatening toxicity at any time, they will be removed from study per the dose modification parameters below. If a subject is able to resume treatment after an interruption of \leq 3 weeks, missed doses will not be made up (i.e. the cycle duration will remain unchanged).

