- h. Complete Blood Count (CBC): Performed on day 1 and 15 of cycles 1 and 2 (+/- 3 days) then day 1 of each cycle (+/-3 days). For patients experiencing significant cytopenias felt possibly related to Topotecan, CBCs should be obtained more frequently (weekly or more frequently) to assess timing for retreatment or need for G-CSF or transfusion support.
- i. Patients **with PD** at end of treatment will be followed every 6 months for 2 years (or until death) for survival (from the last day of treatment). Patients **without PD** at end of treatment will be followed every 6 months for 5 years (or until death) for survival and progression (from the last day of treatment). Follow-up may occur over the phone.
- j. Patients who are removed from study treatment for toxicity should be followed until toxicity resolves to grade 1 or baseline.
- k. Radiology assessment by CT or MRI will be done at Week 6, Week 12, Week 20 and every 8 weeks (+/- 7 days) thereafter. After 1 year of protocol treatment, patient may be switched to scans every 12 weeks (+/- 7 days) at the discretion of the patient and treating physician.
- l. Blood samples for mandatory correlative study will be collected at screening or on Cycle 1 Day 1 prior to treatment, and day 1 of Cycle 2, 3, and 4 , (+/-3 days) as in section 9.1.
- m. Unless otherwise noted, on-therapy windows for testing will be as follows: imaging scans should be completed within +/- 1 week of the target time point, and labs and physical examinations within +/- 3 days of the target time point.
- n. End of treatment visit must occur within 30 days following the last day of treatment, particularly prior to patient starting new treatment.
- o. Patient to call coordinator weekly to report toxicities- if no toxicities to be reported, patient need not call in. Toxicities should be followed for 30 days after last dose of study treatment, however, new toxicities that arise within the 30 day period definitely related to new anti-cancer treatment and NOT related to study treatment do not need to be reported.
- p. ONLY required for patients with prior anthracycline use OR otherwise at risk for left ventricular systolic dysfunction. May be assessed by MUGA or echocardiogram.

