For this project, we will be applying CAPP-Seq to blood and tissue as we have done previously [1,2,7], by isolating DNA from ~10 mL of plasma, inputting ~32 ng into the CAPP-Seq library preparation protocol which starts with adapter ligation, performing PCR, then targeted hybrid capture, and then NGS on a NovaSeq, HiSeq4000 or a NextSeq. We then will analyze the results using the CAPP-Seq or AVENIO bioinformatics pipeline which enables variant-calling and calculation of variant allele fractions (VAFs) which are averaged at each time point to yield the mean VAF. We will use this measure, as well as the ctDNA concentration (VAF x cfDNA concentration) to quantify ctDNA at each time point, and correlate these results with demographic, diagnostic, treatment, and outcomes data.

For Cohort 2:

Sleijfer et al. recently published a translational study in which they evaluated whether cytokine levels in the patients enrolled in EORTC 62043, the phase II study of pazopanib in soft tissue sarcoma, correlated with PFR and OS. They measured levels of several cytokines at baseline and 12 weeks after beginning pazopanib therapy and demonstrated that baseline levels were not predictive, but that high sVEGFR2 and low PIGF were associated with a more favorable PFR at 12 weeks (OR 0.636, 95% CI 0.413-0.977, P=0.039) and (OR 1.081, 95% CI 1.007-1.160, P=0.0318) respectively. There was also a trend toward high sVEGFR2 at week 12 and increased OS and a statistically significant association between low PIGF levels at week 12 and longer OS (HR 1.061, 95% CI 1.025-1.099, P=0.0009) 6.

We propose to measure sVEGFR2 and PIGF levels in blood to both verify the results of Sleijfer et al and to determine if there is an even earlier correlation that can be detected between levels of these cytokines and PFR as well as OS which may allow us to better predict treatment response early on in therapy.

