9.1 Sample Collection Guidelines (please see the lab manual for full details)

Mandatory whole blood samples will be collected at screening or predose on Cycle 1 Day 1, and day 1 of Cycles 2, 3, and 4. Approximately 20 ml of anticoagulated whole blood will be collected in 2 EDTA purple top tubes and 1 SST red top tube at each timepoint. Whole blood for DNA, mononucleated cells, and serum should be immediately prepared from the 2 EDTA purple top tubes and SST red top tube, respectively, and frozen down to -80° C prior to shipment using standard laboratory techniques. Samples should be labeled with the corresponding patient's study ID number, initials, and date of collection.

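### Cohort 2's week-8 and week-12 cytokine samples come largely from patients still on treatment without progression, so the week-12 level says almost nothing about 12-week PFR and later levels need a landmark analysis

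*Combined protocol and SAP*

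**What the plan says.** Section 2.3 sets the cohort 2 sampling times: "To meet this endpoint we will collect samples at baseline, 4 weeks, 8 weeks, and 12 weeks". There are two aims: to verify a published cytokine study in pazopanib-treated soft tissue sarcoma, and, in the words of section 9.0, to "determine if there is an even earlier correlation that can be detected between levels of these cytokines and PFR as well as OS".

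Section 9.0 describes the published study. Cytokines were measured at baseline and 12 weeks, and baseline levels were not predictive. High sVEGFR2 and low PlGF were associated with better PFR at 12 weeks. The OS findings are stated explicitly for week-12 levels. The association to be verified is therefore, on the natural reading, week-12 level against 12-week PFR.

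The operational rules are these:

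- Footnote l of the study procedures schedule has blood "collected at screening or on Cycle 1 Day 1 prior to treatment, and day 1 of Cycle 2, 3, and 4", within 3 days either way. Section 9.1 agrees: "predose on Cycle 1 Day 1, and day 1 of Cycles 2, 3, and 4".
- Section 4.3 lists, among the conditions for treating on day 1 of a later cycle, "No evidence of progressive disease". Section 4.1 ends treatment at progression.
- Footnote k: "Radiology assessment by CT or MRI will be done at Week 6, Week 12, Week 20". Footnote m gives scans a window of one week either way.
- Footnote i allows follow-up after treatment by phone.

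Section 10.3 covers PFR, OS, response and toxicity. It gives no method for any biomarker: no landmark, no time-dependent covariate and no rule for missing samples.

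**The concern.** Whether the week-12 predictor is observed depends heavily on the 12-week outcome. If nearly everyone with a week-12 level is progression-free at week 12, an odds ratio for 12-week PFR rests on a handful of failures who happened to be bled before they were scanned. Reporting it as confirming or refuting the published association would mislead in either direction.

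Two further problems follow. First, looking for the earliest useful time point by setting weeks 4, 8 and 12 side by side compares progressively healthier subsets of the cohort. Second, a patient with a cycle 4 sample has by definition lived to about day 82 or later, usually without progression. Counting PFS or OS from treatment start credits that guaranteed time to the sampled group. A Cox hazard ratio within sampled patients alone, all bled at nearly the same day, changes little with the time origin. Kaplan-Meier curves, medians, and any comparison with unsampled patients or across time points do change.

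**Working it through.** The plan gives no expected sample count or power for this objective, so there is no figure of its own to reproduce.

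**Calendar** (28-day cycles, cycle 1 day 1 = day 1)

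| Event | Target day | Window |
|---|---|---|
| Cycle 2 day 1 draw | 29 | 26–32 |
| Week-6 scan | 42 | 35–49 |
| Cycle 3 day 1 draw | 57 | 54–60 |
| Week-12 scan | 84 | 77–91 |
| Cycle 4 day 1 draw | 85 | 82–88 |

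The cycle 2 draw closes before the earliest week-6 scan, so it is free of scan-based selection. The latest week-6 scan precedes the earliest cycle 3 draw, so a patient who progresses at week 6 and stops has neither a week-8 nor a week-12 sample. The week-12 scan and cycle 4 draw windows overlap, so a patient who progresses at week 12 may or may not have been sampled.

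**Expected failures, n = 36.** Assumption: exponential progression, S(t) = exp(−λt), with 4 months = 121.75 days. Both calibrations come from the osteosarcoma study of a different drug cited in section 1.8.

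- Median 4 months: λ = 0.6931/121.75. S(42) = 0.787 and S(84) = 0.620. Failures by week 6: 36 × 0.213 = 7.7. From week 6 to week 12: 36 × (0.787 − 0.620) = 6.0. Total 13.7.
- 46% at 4 months: λ = 0.7765/121.75. S(42) = 0.765 and S(84) = 0.585. Failures by week 6: 8.5. By week 12: 14.9, so 6.4 in the second interval.

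**Failures with a week-12 level.** None of the week-6 group has one. For the second group, assume the draw is taken only if progression has not yet been found, with dates uniform in their windows.

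- Treating both windows as centred on the same day, the draw comes first with probability 0.50: 6.0 × 0.50 = 3.0 of 13.7.
- With the actual centres (scan day 84, draw day 85, whole days), the probability that the scan falls after the draw is (91 − 85)/15 = 0.40. Simulating scan and draw dates with 400,000 patients per scenario gives 2.6 of 13.7 at the 4-month median and 2.8 of 14.9 (19%) at 46%. These slightly exceed 0.40 times the second group because the scans that follow the draw are the later ones and catch a little more progression.
- Range over assumed 4-month rates: 3.4 of 20.0 (17%) at 31%, which is the 11/36 threshold in section 10.2; 2.1 of 10.7 (20%) at 60%.
- If status is dated strictly at day 84: none with the draw on day 85, and about 0.2 patients using the draw window.

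**Week 8.** At 46%, about 6.5 of the 14.9 failures (43%) have a cycle 3 sample; over the range, 40% to 46%.

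**Landmark sets at 46%.** Progression-free at weeks 4, 8 and 12: about 30, 25 and 21 of 36.

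**The case against.** The strongest counter-argument is that section 4.3 governs giving treatment, not drawing blood. Section 9.1 calls the samples mandatory, and section 4.2.1 puts dosing after visit procedures. A patient scanned just before the cycle 4 visit could be bled before the scan is read. That is fair, and it is why a reader should not infer that week-12 samples exist only for patients who start cycle 4, or that the week-12 contrast cannot be computed. The windows, and any delay in reading scans, allow some sampled failures. The effect is bounded, however. If every patient progressing at the week-12 scan were sampled, that would be 6.0 of 13.7 failures at the 4-month median. The 7.7 week-6 failures would still be missing, so the contrast would remain selected on outcome.

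A reader might also infer that the whole cytokine objective fails. It does not. Baseline and week-4 levels can be related to 12-week PFR, the aim of finding an earlier correlation relies on those earlier draws, and section 2.2.6 defines the osteosarcoma endpoint as time to progression, which suits landmark analysis.

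Nor do the documents support extending the full criticism to ctDNA in cohorts 1 and 3. Sections 2.3 and 9.0 plan only correlation with unspecified outcomes data and name no week-12 test against 12-week PFR. Only the availability limit carries over: at the 55% and 66% rates of section 10.1, 92 × 0.45 = 41 or 92 × 0.34 = 31 patients would not be progression-free at week 12 and would mostly lack that sample.

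Finally, the section 5 schedule table is not visible and section 9.1 defers to a lab manual. The absence of an end-of-treatment draw rests on footnote l and section 9.1.

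**Conclusion.** The concern holds for cohort 2 in a limited form. Late cytokine samples depend largely on remaining on treatment without progression. That leaves about 2 to 3 of roughly 14 to 15 failures with a week-12 level, so the planned verification of the 12-week association cannot be read reliably. Relating week-8 or week-12 levels to PFS or OS from treatment start needs a landmark, and none is stated.

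The counts rest on an exponential model, rates from another drug, uniform visit dates and immediate scan reading. Dropout for toxicity, early death and clinical progression between scans are not modelled; the first two would remove further late samples. The calendar argument about week-6 progressors needs none of the model assumptions, only that sampling stops when treatment stops.

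No primary or secondary conclusion, sample size or decision rule depends on this objective. The priority is minor.

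**What to change.** Amend the analysis wording in sections 2.3, 6.7 and 9.0:

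1. Relate 12-week PFR primarily to the baseline level, the cycle 2 day 1 level and the change between them.
2. Analyse cycle 3 and cycle 4 levels only by landmark: PFS and OS counted from the draw, in patients alive and progression-free at that draw. Week-8 level against week-12 status may be reported if labelled as conditional on reaching cycle 3.
3. Do not claim verification of the association between week-12 level and 12-week PFR.
4. When comparing time points, do not restrict baseline or week-4 analyses of 12-week PFR to patients with a week-12 sample, since that imposes the same selection on them. Make such comparisons on outcomes after the latest landmark used.
5. Apply the same landmark rule if post-baseline ctDNA levels are related to PFS or OS in cohorts 1 and 3.

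This needs no new samples or patients. The cost is that the week-12 contrast is given up and later landmarks have fewer patients. Adding a draw at progression or end of treatment would address the gap directly, but Appendix H records that the study is closed to further accrual, so it would come too late for most or all patients.
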